11.4. Vital Sign Measurements

Vital sign measurements (weight, systolic and diastolic blood pressure, pulse rate, respiration rate and temperature) as well as change from baseline will be summarized descriptively by scheduled time point. The last vital sign measurement on or prior to the date of first dose of study drug will be used as the baseline value. Frequency summaries (shift tables) of shifts from baseline to post-baseline by cycle and to the worst post-baseline value in terms of normal/abnormal will be provided for pulse, respiratory and blood pressure. The normal ranges are defined as: 60-100 beats/minute for pulse, 12 to 16 breaths/minutes for respiratory rate, 90-140 mmHg for systolic blood pressure, and 60-90 mmHg for diastolic blood pressure). Vital sign data collected after the date of the end of treatment visit, last dose date + 28 days, whichever the latest, will not be used for summary. A listing of all vital signs will be provided.

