1.4.1 Risk Assessment

Potential Risk of Clinical Significance	Summary of Data/Rationale for Risk	Mitigation Strategy
Study Intervention - Azacitidine		
Neutropenia and severe infections	In subjects randomized to oral azacitidine 300 mg at 21-day treatment schedule, the most frequent hematological AEs were neutropenia, febrile neutropenia,	To mitigate risk of severe infections, during Cycles 1 and 2 (higher risk period for severe infections) the subjects will receive oral azacitidine for 14 days of a 28-day cycle

Potential Risk of Clinical Significance	Summary of Data/Rationale for Risk	Mitigation Strategy
	
and associated infections. There was an imbalance in incidence of death between the drug and placebo treatment groups. Most of the death cases in the oral azacitidine-treated subjects occurred during the first 56 days on treatment with infections being the leading cause of death. Affected subjects showed lower median ANC at baseline, which could have made them more susceptible for severe infections.
	
schedule. The treatment can be extended to a 21-day schedule after Cycle 2, if a subject did not experience Grade 3 or 4 toxicities requiring dose delay or reductions and if there is no evidence of hematological improvement on 14-day dosing schedule.
 
During the first 2 cycles on treatment subjects' blood counts will be monitored on weekly basis, reducing to biweekly monitoring up to Cycle 12.
 
Guidance for IP dose modification due to toxicities including neutropenia and febrile neutropenia is provided in Section 8.2.4 and Table 2 of the Protocol.
 
A strong recommendation regarding administration of prophylactic fluoroquinolone antibiotics or other recognized prophylactic antibiotics was provided for subjects who develop Grade 4 neutropenia (see Section 9.1).

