11.3. Clinical Laboratory Evaluations

Clinical laboratory values will be presented using the reported units. Change in clinical laboratory results from baseline (last non-missing value on or prior to the date of first dose of the study drug) to each scheduled time point will be provided for the safety population. Clinical laboratory values will be graded according to CTCAE version 4.0 for applicable tests. Shift tables for change in maximum CTCAE grades of high and low lab values, separately, will be provided for the safety population by treatment for those labs that have CTCAE grades. Separate shifts tables will be provided for lowest value by cycle and highest value by cycle. Clinically significant laboratory abnormalities that meet Grade of 3 or Grade 4 criteria according to the CTCAE will be listed and summarized (counts and percentages) by cycle. Laboratory data collected after the date of the end of treatment visit, last dose date + 28 days, whichever the latest, will not be used for summary. Nadirs, the minimum values, of selected hematology parameters, ie. Hgb, platelets, absolute neutrophil count (ANC), white blood cell counts, and RBC, across all cycles and within each cycle will be summarized. The day of nadir will be summarized categorically by frequency of the day of the cycle that the nadir observation occurs, by cycle and treatment. The categories for the days within a cycle are day 1-7, Day 8-14, Day 15-21 and Day >21. The average onset day of nadir across all cycles, the analyte value at nadir by cycle, and the change from baseline to analyte value at nadir will be summarized descriptively by treatment for each selected hematology test.

A separate listing, including only values outside the normal range, if any, will also be provided. A listing of all clinical laboratory values will be provided. Separate listings will be provided for the hematology, blood chemistry, coagulation, urinalysis, erythropoietin, ferritin and serum transferrin saturation laboratory values.

Graphical display of select laboratory parameters over the course of the study will be provided (if needed).

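### Vital-sign shift tables pool low and high values as abnormal, so they cannot show direction of change by arm; temperature has no categorical display

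*SAP*

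**What the plan says.** SAP 11.4 plans three displays of vital signs.

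- **Descriptive summaries.** "Vital sign measurements (weight, systolic and diastolic blood pressure, pulse rate, respiration rate and temperature) as well as change from baseline will be summarized descriptively". These summaries are made for each planned visit.
- **Shift tables.** One comparison with baseline is made for each cycle and another, in the SAP's words, "to the worst post-baseline value in terms of normal/abnormal will be provided for pulse, respiratory and blood pressure". Each of these signs has limits on both sides, as follows: "60-100 beats/minute for pulse, 12 to 16 breaths/minutes for respiratory rate, 90-140 mmHg for systolic blood pressure, and 60-90 mmHg for diastolic blood pressure". Temperature is not among the signs shifted and has no range.
- **Listing.** "A listing of all vital signs will be provided".

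Baseline is fixed: "The last vital sign measurement on or prior to the date of first dose of study drug will be used as the baseline value".

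The preceding section, SAP 11.3, treats laboratory data differently. "Shift tables for change in maximum CTCAE grades of high and low lab values, separately, will be provided" for tests that have CTCAE grades, and there are separate shift tables for the lowest and the highest value by cycle.

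Protocol 10.7 asks only for listings and for descriptive statistics of observed values and changes by treatment group. The vital-sign shift tables are therefore an addition made by the SAP.

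**The concern.** A shift table is there to show movement that averages can hide. Here each range has a lower and an upper limit, but both sides fall into one class. Two kinds of information are lost. A subject who crosses the whole normal range stays in the abnormal-to-abnormal cell. A subject who starts normal and leaves the range is counted, but the table does not say whether the value fell or rose.

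Direction is relevant in this trial. Protocol 1.4.1 reports an imbalance in deaths and says that most deaths on oral azacitidine "occurred during the first 56 days on treatment with infections being the leading cause of death". A fall in pressure and a rise in pressure do not mean the same thing in that setting, and the planned table would report them as one count. The gap on temperature is separate and has no part in the blood-pressure problem: within the vital-sign outputs, temperature is never put into categories.

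**Working it through.** The plan states no figure on this point, so there is none to reproduce. The check applies the SAP's own ranges to illustrative readings, which are assumptions and not trial data.

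**Inputs (SAP 11.4).** Pulse 60 to 100 beats/minute; systolic pressure 90 to 140 mmHg; diastolic pressure 60 to 90 mmHg.

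**Two-class rule, as planned.** A value v is normal if lower limit ≤ v ≤ upper limit, otherwise abnormal.

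**Three-class rule.** A value v is low if v < lower limit, high if v > upper limit, otherwise normal.

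| Sign | Baseline → later | Change | Two classes | Three classes |
|---|---|---|---|---|
| Systolic | 160 → 80 | −80 | abnormal → abnormal | high → low |
| Diastolic | 95 → 50 | −45 | abnormal → abnormal | high → low |
| Systolic | 160 → 162 | +2 | abnormal → abnormal | high → high |
| Diastolic | 80 → 50 | −30 | normal → abnormal | normal → low |
| Pulse | 80 → 125 | +45 | normal → abnormal | normal → high |
| Systolic | 160 → 200 | +40 | abnormal → abnormal | high → high |

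**Crossing the range.** Rows 1 and 3 share a cell under the planned rule, although one is a fall of 80 mmHg and the other a rise of 2. Three classes separate them.

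**Normal at baseline.** Suppose that one arm has L subjects going low and H going high, and the other arm has H going low and L going high. The planned table shows L + H in both arms, so it cannot reveal the difference.

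**What three classes do not recover.** In row 6 the subject worsens further on the side where he or she started and stays in one cell under either rule. Among subjects already out of range, the change of classes helps only those who cross to the other side.

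**Limits of the example.** The missing shift is specific to a sign. A subject with systolic 160 → 80 may still move from normal to abnormal on diastolic pressure (row 4) or pulse (row 5).

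**Temperature.** No classification can be run, because the SAP gives no range.

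**How much the data can show.** Protocol 6.6.3 schedules vital signs on Day 1 of each cycle and at treatment discontinuation. With 28-day cycles and no delay, Cycle 2 Day 1 is 28 + 1 = Day 29 and Cycle 3 Day 1 is 2 × 28 + 1 = Day 57. If Cycle 1 Day 1 supplies the baseline, the first 56 days nominally hold one scheduled cycle reading on treatment.

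**The case against.** The strongest reply is that this is a preference about one descriptive table and that the safety question is answered better elsewhere. Most of that stands. The SAP analyses infection and neutropenia as events of special interest by arm, including serious events, Grade 3 or 4 events, and events leading to death by cycle of onset (11.1.2). It tabulates adverse events by cycle group starting with Cycles 1-2 (11.1.1), cause of death by treatment period (11.2), and neutrophil and white-cell nadirs (11.3). Acute fever or hypotension between Day 1 visits may be absent from scheduled readings whatever classes are used. The laboratory comparison is also imperfect, because the grade shifts in 11.3 rest on CTCAE grades, which 11.4 does not apply to vital signs.

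The reply also disposes of some stronger readings that a reader might infer:

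- *Anyone out of range at baseline cannot show worsening because of the two classes.* Not so. Worsening on the same side is hidden by three classes as well, and 11.4 summarises change from baseline for every sign.
- *Fever goes uncounted in the trial.* Not so. Protocol 1.4.1 lists pyrexia as a known risk, and reported pyrexia would appear in the adverse-event tables of SAP 11.1. The gap lies only in the categorical vital-sign display.
- *The worst value is undefined.* Under two classes it can be resolved: the worst is abnormal if any post-baseline value is abnormal. The question of direction arises only once low and high are separated, which is why the fix uses the lowest and the highest value.

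What the reply does not remove is that the planned table discards direction, which the data contain. Summaries by time point can dilute a few extreme values, and a listing does not compare arms.

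**Conclusion.** The point holds as a minor one. On the SAP's own wording, the shift tables cannot distinguish a subject who crosses from one side of the range to the other from one who stays out of range on the same side, and they merge low and high departures for subjects who start normal. Temperature is handled only descriptively.

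The size cannot be put as a number of subjects. That would need the proportion out of range at baseline on each sign, the proportion who then cross, and the size of the safety population, and the documents give none of these. The 216 randomized subjects are not the right base, because safety summaries use subjects who were dosed.

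A reader might go further and conclude that the infection signal is invisible by arm, or that the SAP departs from the protocol. Neither is supported: the signal has more direct analyses by arm, and the protocol does not require these tables. The primary endpoint, overall survival and the control of type I error are unaffected.

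**What to change.** In SAP 11.4:

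1. Classify each of pulse, respiratory rate, systolic and diastolic pressure as low, normal or high, using the ranges already stated.
2. Replace the single shift to the worst value by two: baseline class to the class of the lowest post-baseline value, and baseline class to the class of the highest. This follows the pattern of SAP 11.3. Use the same three classes in the by-cycle shifts, and present all of them by treatment group.
3. Add temperature, with a normal range written into the SAP. The documents contain no fever cut-off, so the sponsor must choose one and state its source.

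The cost is a change of wording, a re-binning of data already collected, and about one more table per sign. Protocol Amendment 6.0 says that the primary analysis report is final, so for that data cut these would be supplementary tables, labelled as such.

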11.5. Bone Marrow Aspirate Differential and Peripheral Blood Smear

Bone marrow aspirate differential and peripheral blood smear differential, including erythroid precursors, Monocytic lineage, bone marrow blasts (%), ringed sideroblast (%), myeloid lineage, and peripheral blood blasts, as well as their changes from baseline, will be summarized descriptively by cycle and treatment for the Safety population. For each variable, the last observed values on or prior to the date of the first dose date will be used as the baseline value. Bone marrow and peripheral blood data collected after the date of the end of treatment visit, last dose date + 28 days, whichever the latest, will not be used for summary. Individual subject information for bone marrow aspirate and bone marrow biopsy will be listed.

11.6. Electrocardiogram

A 12-lead electrocardiogram (ECG) is required for all subjects at Screening visit. ECG results will be provided in a by-subject listing.

11.7. Pregnancy

A by-subject listing of pregnancy tests and results will be provided for all female patients of childbearing potential.

12. HEALTH-RELATED QUALITY OF LIFE ANALYSIS

The primary objective of the HRQoL assessment is to evaluate the impact of oral azacitidine on HRQoL relative to placebo. Analyses will address mean differences by treatment group on HRQoL scale and subscale scores and treatment group differences in the proportion of subjects who achieve a minimal clinically important difference. Complete analysis plans, including methods to assess responsiveness and minimally important differences will be described in a separate HRQoL statistical plan.

13. HEALTHCARE RESOURCE UTILIZATION

Healthcare resource utilization collected on the CRF healthcare utilization form will be summarized by treatment group and listed for individual subject. Summaries will include number of events, reasons for hospitalization, total number of days hospitalized, the rate of events and days of hospitalized per person-year of exposure and associated relative risk of hospitalization with the corresponding 95% CI.

[REDACTED]

CELGENE PROPRIETARY INFORMATION

[REDACTED]

15. INTERIM ANALYSIS

15.1. General Information

An independent Data Monitoring Committee (DMC) with multi-disciplinary representation has evaluated safety during the course of the study in compliance with a prospective charter. The DMC comprised of medical oncologists/hematologists with experience treating MDS and a statistician, all of whom were not otherwise involved in the study as investigators. An independent statistician generated critical safety reports for the DMC to review periodically. The DMC chairperson might convene formal DMC meetings if there were safety concerns. The Sponsor can also request a DMC review of safety data. The DMC responsibilities, authorities, and procedures were documented in the DMC charter, which were endorsed and signed by the DMC prior to the first data review meeting.

15.2. Statistical Approaches for Control of Alpha

An interim analysis of the OS endpoint will be performed when all 216 subjects have completed 12 months of double-blind treatment or discontinued before reaching 12 months of double-blind treatment (100% information for the primary endpoint), whichever occurs first. It is projected that approximately 68% of the expected total deaths will have occurred at the time of the interim analysis. An O'Brien-Fleming group sequential boundary with a Lan-Demets alpha spending function will be used to preserve the overall alpha level at 0.05 for testing the OS endpoint. The required (two-sided) significance levels are estimated to be 0.013 at the interim and 0.037 at the final analysis for OS assuming 68% of the events have occurred, but the actual levels used will depend on the actual number of events at the time of the interim analysis.

In order to preserve the overall alpha level at 0.05 across the RBC transfusion independence and OS endpoints, formal statistical inference for the OS analyses can only be made if superiority of oral azacitidine is demonstrated for the primary efficacy endpoint, RBC transfusion independence, at the two-sided 0.05 significance level.

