4.4. Sample Size

The basis for the power and sample size determination will be a test of the equality of the overall survival curves between the oral azacitidine and placebo treatment groups using a stratified log-rank test. Assuming a median OS of 18 months in the placebo treated group ([Garcia-Manero, 2008a](#)), which takes into account possible cross-over outside of the protocol of placebo treated

subjects to active treatment during the observation period, and a median OS of 25.7 months (43% improvement) in the oral azacitidine treated group, 216 subjects (108 in each group) would have approximately 72% power to detect a constant hazard rate ratio of 0.70 using a two-sided log rank test with overall significance level of 0.05. It is assumed that the OS distribution is exponential with a constant failure (hazard) rate and that accrual is uniform during the accrual period (56 months) with an overall drop-out rate of 5% from both treatment groups. Full information necessary for a log rank test to have 72% power will be achieved when approximately 205 deaths have occurred in both treatment groups, which is expected approximately 134 months after randomization of the first subject into the study.

An interim analysis of the OS endpoint will be performed and reported when all subjects have completed 12 months [52 weeks (364 days)] of double-blind treatment or have been discontinued from treatment (see Section 15).

While 56 days (8 weeks) is the standard response criteria for hematologic improvement (IWG 2006 criteria; Cheson, 2006; Appendix E), limited information is available on the target population for estimating the response rate for the primary endpoint of RBC transfusion independence maintained for ≥ 84 days (12 weeks).

A total sample size of 216 subjects (108 in the active treatment group and 108 in the placebo group) will have approximately 99% power to detect the difference between a response rate of 0.30 in the active treatment group and a response rate of 0.05 in the placebo group, and approximately 70% power to detect the difference between a response rate of 0.15 in the active treatment group and a response rate of 0.05 in the placebo group. The power calculations for response rate are based on a two-sided alpha of 0.05 and test statistics on the difference of proportions using an un-pooled estimate of variance.

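### The final OS significance level of 0.037 is the alpha left over after the interim; the stated O'Brien-Fleming/Lan-DeMets method gives a threshold of about 0.046

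*SAP*

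**What the plan says.** SAP section 15.2 plans one interim analysis of OS, when all 216 subjects have completed 12 months of double-blind treatment or stopped earlier, and one final analysis. The boundary is of O'Brien-Fleming type, described as a "group sequential boundary with a Lan-Demets alpha spending function will be used to preserve the overall alpha level at 0.05". The projection for the first look is that "approximately 68% of the expected total deaths will have occurred at the time of the interim analysis". On the levels the SAP states: "The required (two-sided) significance levels are estimated to be 0.013 at the interim and 0.037 at the final analysis for OS". It makes both figures conditional on that 68% fraction and adds a proviso: "the actual levels used will depend on the actual number of events at the time of the interim analysis".

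Protocol section 10.8 gives the same method, the same projected fraction, the same two levels and the same proviso. Neither document calls 0.037 an increment of alpha; both present it as a significance level of the same kind as 0.013.

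For power, SAP section 4.4 and protocol section 10.3 claim "approximately 72% power to detect a constant hazard rate ratio of 0.70", with full information when "approximately 205 deaths have occurred in both treatment groups".

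**The concern.** Two figures that add up exactly to 0.05 are a warning sign in a two-look design. Nominal levels from an O'Brien-Fleming-type boundary add up to more than the overall alpha, because the test statistics at the two looks are positively correlated and part of the final rejection region has already been counted at the interim. A pair that sums to 0.05 suggests that the second number was obtained by subtraction.

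OS is the only endpoint besides the primary that has alpha control (SAP section 10.2), so this figure is a confirmatory decision threshold. If it is used as printed, a final OS p-value between 0.037 and 0.046 would be declared non-significant although the plan's own method declares it significant. The stated power would then not be reached either.

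**Working it through.** **Inputs**
- Overall two-sided alpha 0.05, O'Brien-Fleming-type Lan-DeMets spending, information fraction t = 0.68 (SAP 15.2, protocol 10.8).
- 205 deaths at full information, hazard ratio 0.70, 1:1 allocation (SAP 4.3 and 4.4, protocol 10.3).
- 0.68 × 205 = 139.4 deaths at the interim.

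**1. Interim level (the plan's figure reproduces).** Two-sided spend at t is 4 × [1 − Φ(z₀.₉₈₇₅ / √t)].
- z₀.₉₈₇₅ = 2.2414; √0.68 = 0.8246; ratio = 2.7181.
- 4 × 0.003283 = 0.0131, so c₁ = 2.480.

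This matches the printed 0.013, which confirms that the right spending function has been identified.

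**2. Alpha left for the final look.** 0.05 − 0.0131 = 0.0369, which rounds to the printed 0.037.

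**3. Final nominal level under the stated method.** Under the null, (Z₁, Z₂) is bivariate normal with correlation √0.68 = 0.825. Solve P(|Z₁| < 2.480 and |Z₂| < c₂) = 0.95. The solution is c₂ = 1.9956, a two-sided level of **0.0460**.

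**4. Could another reading give 0.037?**

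| Boundary at t = 0.68 | Interim | Final |
|---|---|---|
| Lan-DeMets O'Brien-Fleming type (as stated) | 0.0131 | 0.0460 |
| Same form, spending two-sided 0.05 directly | 0.0175 | 0.0436 |
| Classical O'Brien-Fleming | 0.0150 | 0.0450 |
| Lan-DeMets Pocock type | 0.0387 | 0.0245 |

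None gives 0.013 with 0.037. Nor does a different interim timing: under the stated method the final level is 0.0466, 0.0455 and 0.0442 at t = 0.65, 0.70 and 0.75, and it stayed above 0.039 at every fraction checked from 0.50 to 0.98.

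**5. Effect of using 0.013/0.037 literally (t = 0.68, 205 deaths).** Under HR 0.70 the drift at full information is |ln 0.70| × √(205/4) = 2.553. The critical hazard ratio is exp(−2c₂/√205).

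| | 0.013 / 0.037 (c₂ = 2.086) | 0.013 / 0.046 (c₂ = 1.996) |
|---|---|---|
| Overall two-sided type I error | 0.0417 | 0.0500 |
| Two-look power at HR 0.70 | 68.8% | 71.8% |
| Critical HR at the final analysis | 0.747 | 0.757 |

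**6. Check on the plan's 72%.** A single look at 0.05 with 205 deaths gives Φ(2.553 − 1.960) = 72.4%. The stated power therefore agrees with a fixed design (72.4%) and with the correct two-look boundary (71.8%), but not with 0.013/0.037 (68.8%).

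**The case against.** The strongest reply is that the binding rule is the method and not the illustrative numbers. The levels are described as estimates, they are to be recalculated from the actual number of deaths, and SAP section 10.2.1 says the final p-value will be adjusted for the interim to preserve 0.05. Someone who implements Lan-DeMets spending correctly would never use 0.037, and the 72% power was not built on it. The error is also conservative. It concerns a key secondary endpoint tested only if the primary succeeds, and it could change a conclusion only in a p-value window about 0.009 wide (0.046 − 0.037). The interim level, which governs the only OS look this SAP covers, is right.

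Much of this stands. There is no false-positive risk, and the loss of power arises only if 0.037, or the subtraction behind it, is actually applied. But the proviso does not rescue the figure, because the SAP states it for 68% of events and it is wrong at that fraction. The text gives no formula for the recalculation, so an analyst following the example could well subtract the alpha spent. At 75% information that would give 0.031, against a correct 0.044.

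A further objection is that 0.046 is itself tied to 68% information and a final look at 205 deaths. That is also true. Amendment 6.0 (protocol Appendix J) shortens survival follow-up in the Extension Phase to 35 ± 7 days after treatment discontinuation, so 205 deaths may not be reached. If 0.0131 was spent at 139 deaths and all remaining alpha is used at 150 to 180 deaths, the final level would be about 0.0498 to 0.0476. This is a reason to keep the recalculation sentence. It does not support 0.037, which lies further from these values than 0.046 does.

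**Conclusion.** The concern holds. Under the stated method and at the stated 68% information, the final nominal two-sided level is 0.046. The printed 0.037 is incremental alpha presented as a decision threshold. Used literally, it leaves about 0.008 of the 0.05 unused (0.0500 − 0.0417), costs 3 percentage points of power at HR 0.70 (71.8% to 68.8%), and requires an observed hazard ratio of 0.747 instead of 0.757.

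These sizes assume 205 deaths at the final analysis, about 139 at the interim, proportional hazards and the usual normal approximation for the log-rank statistic. The error is conservative and harmful only if the number is taken at face value. It should be corrected, but it does not threaten the validity of a positive OS claim.

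**What to change.** In SAP section 15.2 and protocol section 10.8, replace 0.037 with 0.046, so that the estimated levels at 68% information read 0.013 at the interim and 0.046 at the final analysis. If 0.037 is kept, label it as the alpha increment spent at the final look and give 0.046 beside it as the p-value threshold.

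Keep the sentence on recalculation. Add that the final critical value is solved from the joint distribution of the two test statistics, using the alpha actually spent at the interim and the deaths actually observed at both looks.

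The cost is one number and one sentence in two documents, with no operational consequence. The correction follows from the method already specified, so the design does not change. Because it relaxes a printed threshold, it should be documented before the final OS data are seen, so that it cannot be taken for a post hoc change.
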